### **11.3. Eliciting Adverse Event Information**

At every study visit, patients must be asked a standard, nondirected question, such as, “How have you been feeling since your last visit?” to elicit any medically related changes in their well-being. They may also be asked if they have been hospitalized, had any accidents, used any new medications, or changed concomitant medication regimens (including prescription drugs, over-the-counter medications, vitamins, herbal products, and minerals). Responses must be documented in the source documents.

In addition to patient observations, AEs must be documented for any clinically significant diagnosis resulting from abnormal laboratory test values that are monitored per patient’s standard of care, physical examination findings, or from other documents that are relevant to patient safety.

#### **11.4. Assessment of Causality**

The investigator must use the following classifications and criteria to characterize the relationship or association of the study drug in causing or contributing to the AE:

Not Related: This relationship suggests that there is no association between the study drug and the reported event.

Unlikely Related: This relationship suggests that the temporal sequence of the event with study drug administration makes a causal relationship improbable and/or other factors also provide plausible explanations.

Possibly Related: This relationship suggests that treatment with the study drug caused or contributed to the AE. That is, the event follows a reasonable temporal sequence from the time of study drug administration, and/or, follows a known response pattern to the study drug, but could have been produced by other factors.

Probably Related: This relationship suggests that a reasonable temporal sequence of the event with study drug administration exists and, based upon the known pharmacological action of the drug, known or previously reported adverse reactions to the drug or class of drugs, or judgment based on the investigator's clinical experience, the association of the event with study drug administration seems likely.

Definitely Related: This relationship suggests that a definite causal relationship exists between the drug administration and the AE, and other conditions (*e.g.*, concurrent illness, progression/expression of disease state, or concurrent medication reaction) do not appear to explain the event.

#### **11.5. Assessment of Severity**

The investigator will grade the severity of the AEs as mild, moderate, or severe using the following definitions:

Mild: Symptoms causing no or minimal interference with usual social and functional activities;

Moderate: Symptoms causing greater than minimal interference with usual social and functional activities;

Severe: Symptoms causing inability to perform usual social and functional activities.

#### **11.6. Recording Adverse Events**

All conditions present prior to the administration of the first dose of study drug (Day 1) in a previous study with bardoxolone methyl should be documented as medical history in a previous study with bardoxolone methyl. After the first dose, documentation of AEs shall continue until 30 days following administration of the final dose of study medication under this protocol (*i.e.*, through the End-of-Treatment visit), regardless of the relationship of the AE to study drug. Information to be collected will include type of event, date of onset, date of resolution, investigator-specified assessment of severity and relationship to study drug, seriousness, as well as any action taken.

While an AE is ongoing, changes in the severity (*e.g.*, worsening and improving) should be noted in the source documents, but when documenting the AE, only the total duration and greatest severity should be recorded in the eCRF. AEs characterized as intermittent will require documentation of onset and duration.

All drug-related (possibly, probably, or definitely related, see [Section 11.4](#)) AEs and abnormal laboratory test results reported or observed during the study must be followed to resolution (either return to baseline or within normal limits). All other AEs will be followed through the final visit indicated in [Table 3](#), as appropriate.

AEs resulting from concurrent illnesses, reactions to concurrent illnesses, reactions to concurrent medications, or progression of disease states must also be reported. Preexisting conditions (present before the start of the AE collection period) will be considered concurrent medical conditions and should NOT be recorded as AEs. However, if the patient experiences a worsening or complication of such a concurrent condition, the worsening or complication shall be recorded as an AE. Investigators shall ensure that the AE term recorded captures the change in the condition (*e.g.*, “worsening of...”). Any improvement in condition shall be documented per [Section 9.10.7](#).

Each AE shall be recorded to represent a single diagnosis. Accompanying signs (including abnormal laboratory test values) or symptoms shall NOT be recorded as additional AEs. If a diagnosis is unknown, sign(s) or symptom(s) shall be recorded as an AE(s). Changes in laboratory test values will only be considered AEs if they are judged to be clinically significant (*i.e.*, if some action or intervention is required or if the investigator judges the change to be beyond the range of normal physiological fluctuation). If abnormal laboratory test values will be the result of pathology for which there will be an overall diagnosis (*e.g.*, increased creatinine levels in renal failure), only the diagnosis shall be reported as an AE.

Elective procedures (surgeries or therapies) that will be scheduled prior to the start of AE collection will not be considered AEs. These elective procedures shall not be recorded as AEs, but shall be documented in the patient’s source documents as elective (*e.g.*, elective periodontal surgery). However, if a pre-planned procedure will be performed early (*e.g.*, as an emergency) because of a worsening of the preexisting condition, the worsening of the condition shall be captured as an AE.

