**Table 3: Schedule of Assessments**

Assessment \ Study Week (Day)	Day 1 a	Week 1 (Phone) Day 3±2	Week 1 Day 7±3	Week 2 (Phone) Day 10±2	Week 2 Day 14±3	Week 3 (Phone) Day 21±2	Week 4 Day 28±3	Week 4 (Phone) Day 31±2	Week 5 (Phone) Day 38±2	Week 6 Day 42±3	Week 8 Day 56±3	Week 24±3, Every 24 Weeks	End of Study Visit b
Informed consent	X												
Inclusion/Exclusion	X												
Prior and Concomitant medications	X c	X	X	X	X	X	X	X	X	X	X	X	X
Current PAH background medications	X c	X	X	X	X	X	X	X	X	X	X	X	X
Weight at home	X	X	X	X	X	X	X	X	X	X	X		
Weight in clinic	X c		X		X		X			X	X	X	X
Vital sign measurements	X c		X		X		X			X	X	X	X
Physical examination	X c		X		X		X			X	X	X	X
Pregnancy test d	X c											X	
Dispense study drug	X						X					X	
Collect study drug							X					X	X
Telephone contact		X		X		X		X	X				
Adverse event collection	X c	X	X	X	X	X	X	X	X	X	X	X	X
Clinical Chemistries f	X c		X		X		X			X	X	X	X
BNP and/or NT-Pro BNP	X c		X		X		X			X	X	X	X
6-min walk test	X c											X	X
Dyspnea and fatigue g	X c											X	X
WHO functional class	X c											X	X

a On Day 1, all procedures should be performed before study drug administration for patients who are treatment-compliant and have previously participated in clinical studies with bardoxolone methyl.

b After the Week 24 visit, patients will continue to be assessed in person every 24 weeks. The End of Study visit should occur within 30 days after the patient receives their final dose of study medication under this protocol. Patients who will be discontinued from the study prior to the completion of the study must also complete all End-of-Study assessments.

c Day 1 assessments should be performed as part of End-of-Treatment or Follow-up visit procedures from a prior study with bardoxolone methyl.

d A serum pregnancy test will be performed at any point in time if a pregnancy is suspected. All other pregnancy assessments will be urine pregnancy tests. Additional pregnancy assessments will be performed more frequently if required by local law or requested by local health authorities or IRBs/ECs.

e AE assessments on Day 1 should be performed following study drug administration.

f Clinical chemistries will be analyzed locally.

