### **8.3. Patient Discontinuation and Termination**

Patients have the right to discontinue study drug or withdraw from the study at any time for any reason, without prejudice to their medical care. Furthermore, the investigator may discontinue a patient from study drug. Consultation with the medical monitor should occur prior to study drug discontinuation or withdrawing a patient from the study. The reason for a patient's discontinuation from study drug or study termination will be recorded in the electronic case report form (eCRF).

Discontinuation refers to a patient's stopping administration of study drug and all study assessments and visits. Reasons for study drug discontinuation may include the following:

- Occurrence of an AE or change in medical status that will lead the investigator to be concerned about the patient's welfare;
- Administrative reasons (*e.g.*, inability to continue);
- Sponsor termination of the study;
- Voluntary withdrawal;
- Females who become pregnant during the study;
- Premature termination or suspension of an investigational site;
- Loss to follow-up;
- Death;
- Withdrawal of consent.

Patients must discontinue study drug if any of the following occur.

- ALT or AST > 8X ULN;
- ALT or AST > 5X ULN for more than 2 weeks;
- ALT or AST > 3X ULN and (total bilirubin > 2X ULN or International Normalized Ratio [INR] > 1.5);
- ALT or AST > 3X ULN with the appearance of fatigue, nausea, vomiting, right upper quadrant pain or tenderness, fever, rash, and/or eosinophilia (> 5%).

Patients who discontinue from the study will be asked to complete the End-of-Study procedures noted in [Table 3](#).

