### **11.2. Adverse and Serious Adverse Events**

#### **11.2.1. Definition of Adverse Events**

##### **11.2.1.1. Adverse Event**

An AE is defined as any untoward medical occurrence in a patient regardless of its causal relationship to study drug. An AE can be any unfavorable and unintended sign (including any clinically significant abnormal laboratory test result), symptom, or disease temporally associated with the use of the study drug, whether or not it is considered to be study-drug related. Included in this definition are any newly-occurring events or previous condition that has increased in severity or frequency since the administration of study drug.

All AEs that are observed or reported by the patient during the study (from time of administration of the first dose at the Day 1 visit until the final visit indicated in [Table 3](#)) must be reported, regardless of their relationship to study drug or their clinical significance.

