##### **11.2.1.2. Serious Adverse Event**

An SAE is any AE occurring at any dose and regardless of causality that:

- Results in death;
- Is life-threatening;
- Requires inpatient hospitalization or prolongation of existing hospitalization;
- Results in persistent or significant incapacity or substantial disruption of the ability to conduct normal life functions;
- Is a congenital anomaly or birth defect in an offspring of a patient taking study drug;
- Is an important medical event.

The term "life-threatening" refers to an event in which the patient was at immediate risk of death at the time of the event. It does not refer to an event that hypothetically might have caused death if it were more severe.

Important medical events are those that may not meet any of the criteria defined above; however, they may be considered serious when, based upon appropriate medical judgment, they may jeopardize the patient and may require medical or surgical intervention to prevent one of the other outcomes listed in the SAE definition.

Pregnancy is not considered an AE; however, information will be collected for any pregnancies that occur during the study (from the time of the first dose of study drug until the final visit indicated in [Table 3](#), as appropriate). Certain pregnancy outcomes will require submission as an SAE (See [Section 9.8](#)).

The investigator is responsible for reporting to Reata or designee all AEs and SAEs that are observed or reported by the patient during the study (from the time of administration of the first dose of study drug until the final visit indicated in [Table 3](#), as appropriate), regardless of their relationship to study drug or their clinical significance.

The Sponsor, or the Contract Research Organization (CRO) on the behalf of the Sponsor, must be notified immediately regarding the occurrence of any SAE that occurs after the patient receives the first dose of study drug and throughout the study, regardless of study drug administration, including SAEs resulting from protocol-associated procedures, as defined in relevant legislation. The procedures for reporting all SAEs, regardless of causal relationship, are as follows:

- Record the SAE on the AE eCRF and complete the “Serious Adverse Event Report” form within the electronic database;
- In the event the electronic database is not functional, a paper SAE form will be available for the reporting of SAEs.

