6.6.3. Missing Start and Stop Dates for Adverse Events

Treatment-emergent adverse events (TEAEs) are events that either:

- Had a date of onset on or after the date of the date of first dose of study drug and not more than 30 days after the date of the last dose of study drug, or
- Had no recorded date of onset with a stop date after the first dose of study drug, or
- Had no recorded date of onset or stop date.

Adverse events with incomplete start dates are considered after the date of first dose if:

- Day and month are missing, and the year is equal to or after the year of the first date of study drug administration;
- Day is missing and the year is after the year of the first date of study drug administration;
- Day is missing and the year is equal to the year of the first date of study drug administration and the month is equal to or after the month of the first date of study drug administration; or
- Year is missing.

Adverse events with incomplete start dates are considered on or within 30 days of last dose, if:

- Day and month are missing, and the year is equal to or before the year of the date of last dose of study drug plus 30 days;
- Day is missing and the year is equal to or before the year of the date of last dose of study drug plus 30 days, and month is equal to or before the month of the date of last dose of study drug plus 30 days;
- Year is missing.

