9.1. Adverse Event Preferred Term and Body/Organ System Summary Tables

AEs are summarized by treatment analysis group as defined by the safety analysis set. General considerations for AE summaries and calculations are:

- Multiple events by preferred term (PT) and system organ class (SOC) are counted once only per patient for each treatment analysis group.
- For summaries by severity, only the most severe event is counted per patient for each treatment analysis group.
- For summaries by relationship, for frequency counts by patient, only the most related event is counted per patient for each treatment analysis group.
- An AE with a missing resolution date or incomplete date that is not identified as continuing is assumed to be continuing and no duration is calculated.
- Only treatment-emergent adverse events (TEAEs) are included in summaries.

AEs are coded using MedDRA (Medical Dictionary for Regulatory Activities) version 19.0. In MedDRA, each verbatim term is mapped to a preferred term and high level term (HLT), which is then mapped to a system organ class. Tables and listings present data at the SOC and PT level.

Treatment-emergent adverse events (TEAEs) are events that either:

- Had a date of onset on or after the date of the date of first dose in the RANGER study and not more than 30 days after the date of the last dose of study drug in the RANGER study, or
- Had no recorded date of onset with a stop date after the first dose of study drug, or
- Had no recorded date of onset or stop date.

Adverse events with a date of onset in LARIAT or CATALYST that continued during the RANGER study are not considered TEAEs.

In addition, adverse events which occurred >30 days after the date of last dose of study drug are listed as late-onset AEs (LOAEs). These are adverse events that had a date of onset more than 30 day after the date of the last dose of study drug.

The investigator grades the severity of the AEs as mild, moderate, or severe as defined in the study protocol Section 11.5.

Association or relatedness to the study medication are graded by the investigator according to criteria specified in Section 11.4 of the study protocol.

As defined in the protocol and captured on the CRF, a serious adverse event (SAE) is an adverse event that results in any of the following:

- Death;
- A life-threatening adverse drug experience;
- Inpatient hospitalization or prolongation of existing hospitalization;

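### The protocol gives two different end points for adverse event collection, so the SAP's 30-day treatment-emergent window may be only partly observed when the End of Study visit is early

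*Protocol*

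**What the plan says.** The protocol states the end of AE collection in three places.

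- Section 11.2.1.1 requires AEs to be reported "from time of administration of the first dose at the Day 1 visit until the final visit indicated in" Table 3.
- Section 11.2.1.2 gives the same period for AEs and SAEs: "from the time of administration of the first dose of study drug until the final visit indicated in" Table 3.
- Section 11.6 gives a different one: "documentation of AEs shall continue until 30 days following administration of the final dose of study medication under this protocol". It then explains this in parentheses as "through the End-of-Treatment visit".

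The last column of Protocol Table 3 is the End of Study visit. Footnote b sets its timing: "The End of Study visit should occur within 30 days after the patient receives their final dose of study medication under this protocol". Table 3 has no End-of-Treatment column; footnote c uses that name for a visit in the prior study. No contact is scheduled after the End of Study visit, and Section 8.3 says "Discontinuation refers to a patient's stopping administration of study drug and all study assessments and visits", with only the End-of-Study procedures then requested.

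SAP 9.1 defines a treatment-emergent AE as one with onset on or after the first RANGER dose and "not more than 30 days after the date of the last dose of study drug in the RANGER study". SAP 6.6.3 has the same limit: "not more than 30 days after the date of the last dose of study drug". Under SAP 6.2 and 9.1.2 the AE tables give numbers and percentages of patients, and the denominator is the patients who received study drug.

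**The concern.** Thirty days is the latest date for the End of Study visit, not its fixed date. Whenever the visit falls sooner, Section 11.2.1 closes reporting before Section 11.6 does and before the SAP's window ends. The parenthesis in 11.6 suggests that the authors took the two points to be the same, but it names a visit that this study does not have.

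AE and SAE frequency is part of the primary safety endpoint. A patient with an early final visit stays in the denominator for the full 30-day window although the site may have stopped recording. An event in the uncovered days is then absent from the table, and nothing in the planned output separates this from a patient who was followed and had no event. Whether such events are captured can also depend on which section a site applied. Patients who stopped soon after starting are proportionately most exposed, because the post-dose window is a large part of their total period.

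**Working it through.** The study is descriptive and the plan states no figure to reproduce. The check is arithmetic on the windows.

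**Inputs**
- Treatment-emergent window after the last dose: 30 days (SAP 6.6.3 and 9.1).
- Day of the final visit after the last dose: d, with 0 ≤ d ≤ 30 (Protocol Table 3, footnote b).
- Time on drug: T days. The values below are assumed for illustration; they correspond to Weeks 4, 8, 24, 48 and 96.

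**Post-dose days covered if a site applies 11.2.1**

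Covered = d; uncovered = 30 − d; share covered = d/30.

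| Final visit (day d) | Covered | Uncovered | Share covered |
|---|---|---|---|
| 0 | 0 | 30 | 0% |
| 3 | 3 | 27 | 10.0% |
| 7 | 7 | 23 | 23.3% |
| 14 | 14 | 16 | 46.7% |
| 21 | 21 | 9 | 70.0% |
| 28 | 28 | 2 | 93.3% |
| 30 | 30 | 0 | 100% |

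**Uncovered share of the patient's whole treatment-emergent period**

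Share = (30 − d)/(T + 30). For example, d = 14 and T = 56 gives 16/86 = 18.6%.

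| T (days, assumed) | d = 0 | d = 14 | d = 28 |
|---|---|---|---|
| 28 | 51.7% | 27.6% | 3.4% |
| 56 | 34.9% | 18.6% | 2.3% |
| 168 | 15.2% | 8.1% | 1.0% |
| 336 | 8.2% | 4.4% | 0.5% |
| 672 | 4.3% | 2.3% | 0.3% |

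**Imputed end dates**

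SAP 6.6.4 sets a missing treatment end date or study end date to 30 March 2020. If both are missing, d = 0 by construction. The treatment-emergent window then runs to 29 April 2020 (30 March + 30 days), and none of its 30 post-dose days lies before the recorded study end.

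**With one end point at day 30**

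If AEs are collected to day 30 whatever the date of the visit, the uncovered time is 0 for every d.

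**The case against.** The strongest reply is that both texts can be obeyed. Section 11.6 is the recording section and is mandatory, 11.2.1 does not forbid recording later events, and the parenthesis in 11.6 shows that one end point was meant. A site reading the whole protocol would use the longer period. This stands in part: loss is certain only where a site applies 11.2.1, and under 11.6 an event volunteered after an early visit would still be recorded. It does not remove the problem, because 11.2.1 states a definite earlier stop and no scheduled contact elicits events after the visit.

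Other text softens the point without closing it.
- Section 11.2.1.2 also requires SAE notification throughout the study, whether or not the patient is still on drug.
- Sections 11.2.1.2, 11.6 and 11.7 require follow-up of SAEs, and 11.6 of drug-related AEs. That concerns events already known and does not find new ones.
- SAP 9.1 lists events with onset beyond 30 days as late-onset, so its authors expected some later reports.
- SAP Table 3 targets a follow-up assessment at 28 days after the last dose, window 14 to 35. This suggests that very early visits were not intended, but it is an analysis window and does not schedule anything.
- Footnote b of SAP Table 2 ties the End-of-Study visit to commercial availability and not to the last dose, so it does not secure day-30 coverage either.

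A reader might infer that uncovered days enter the analysis as event-free time at risk and bias an incidence rate. The SAP does not support that: it plans no person-time, exposure-adjusted or time-to-event analysis of AEs. A reader might also infer an average loss of 15 of the 30 days. That needs visits spread evenly over days 0 to 30, and nothing in the documents supports such a spread.

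**Conclusion.** The inconsistency is real and touches the primary safety endpoint. Where the End of Study visit precedes day 30 and the site stops at that visit, 30 − d post-dose days are not ascertained, and the descriptive AE and SAE counts can only be too low. The loss per patient runs from 0 days (visit on day 30) to 30 days (visit on the day of the last dose). As a share of the whole period it is small after long treatment and can be large after short treatment.

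The number of missed events, and the number of patients affected, cannot be computed: the documents give neither the dates of the End of Study visits nor which section sites followed. The percentages by time on drug rest on assumed durations. There is no comparator, test, alpha or sample size calculation for this to disturb; the effect is on the completeness of descriptive counts. It should be corrected because it is cheap to correct, and disclosed where it no longer can be.

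**What to change.** **Protocol.** Reconcile 11.2.1.1, 11.2.1.2, 11.6 and Table 3 to one end point for AE and SAE collection: 30 days after the final dose, which matches 11.6 and the SAP. Where the End of Study visit was earlier, add a brief telephone AE check at day 30; the trial already uses telephone contacts. Remove or correct the End-of-Treatment visit wording in 11.6.

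**SAP and study report.** State the number of patients whose last AE contact was before day 30 after the last dose, and give the distribution of days from last dose to last AE contact. Identify patients whose end dates were imputed, since their dates do not show when contact ended.

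The SAP (version 2.0, 5 June 2020) records that the study was terminated on 30 March 2020. For data already collected the call can no longer be added, and the disclosure is the remedy still available. The protocol change applies to any continuing or reused text.

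**Cost.** A wording clarification, one short call for each patient with an early final visit, and one extra summary.
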